In human studies, single-dose intranasal OXT administration is associated with enhanced emotion recognition/mentalizing²⁶, face identity²⁷, and increased attention to the eye region²⁸. In ASD, studies find reduced plasma OXT levels²⁹, absence of normal developmental increase in oxytocin blood levels with age^{30,31} and variations in the OXT receptor (OXTR)^{32,33}. The greatest excitement has surrounded replicated findings of improved attention to the eye region, mentalizing abilities, and partner preference from single-dose OXT challenge studies in ASD³⁴⁻³⁶. The effects of intranasal oxytocin (INOXT) and its ability to cross the BBB have yet to be determined. INOXT has been shown to affect functional responses in several brain regions including the medial prefrontal cortex, anterior insula, orbitofrontal cortex, amygdala, and ventral striatum.

The convergence of evidence on the impact of OXT/AVP on social behaviors has fueled several investigations of the therapeutic potential of these compounds in neuropsychiatric conditions characterized by social impairment. The vast majority of human studies have been conducted on OXT compounds. Pilot data from oxytocin monotherapy trials indicate daily, intranasal OXT is safe and feasible in adult^{37,38} and pediatric populations^{37,39} delivered over a period of 6 weeks^{37,40} to seven months³⁸. The applicant and colleagues recently published on a dose-finding, safety trial of intranasal OXT in 15 adolescents with ASD⁴⁰. Four doses were tested every two weeks for 12 weeks. Follow-up testing was conducted at 16 and 24 weeks. Mild to moderate side effects were reported including irritability, headache, upper respiratory infections, and decreased appetite. In this small open-label trial, significant pre-post changes were found on measures of social cognition, social behavior, anxiety and repetitive behaviors with carry-over effects found at 3-month follow-up on social cognition, repetitive behavior, and functional communication skills. Overall, preliminary findings from multi-dose OXT studies support medium to small effects but require replication in well-powered, controlled trials⁴¹.

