3.1. Study Design

This is a two-phase, 3 year, randomized, single-blind, parallel group, contact controlled pilot trial of OXT augmentation of CBI groups in youth with ASD. Phase 1 (n=10) is an initial development trial to refine manuals, procedures, and outcome evaluations. Phase 2 (n=70) will evaluate feasibility, safety, and preliminary efficacy of ION-ASD relative to the contact control (i.e. social play group). All participants are expected to be outpatients and will participate in a 12-session group therapy, with a follow-up study visit at 24 weeks. Evaluations will be conducted at four time points: Screening, Baseline, Endpoint (week 12), and Follow-up (1-month & 3-months post-treatment).

Each phase will randomly assign in a 1:1 ratio to either ION-ASD or control in blocks of 10. Efficacy outcomes will be evaluated by both caregiver report and blinded independent evaluators (IE); safety assessments will be conducted by unblinded treating medical clinicians (Medical TC). Caregivers and participants will be instructed to conceal group assignment from IEs. IEs, participants, and caregivers will also be instructed on reporting strategies should group assignment be revealed. Corrective action plans in these scenarios will be employed if necessary and include changing IE raters and flagging data. IEs will be asked to “guess” patient conditions at the end of the trial to evaluate integrity of the blind.

Medical TCs will monitor side-effects using weekly ratings with the participant and caregiver. Clinical IEs will evaluate global functioning and social communication skills. Neurocognitive IEs will conduct blinded neurocognitive assessments (see Appendix A: Time & Events Schedule).

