3.6. Blinding/Unblinding

Given the nature of behavioral intervention trials, concealing treatment allocation to participants and treating clinicians is not possible. Independent evaluators (IEs) will conduct blinded CGI ratings at baseline, midpoint, endpoint, and follow-up visits. IEs will be instructed to not ask about treatment allocation and will also be asked to predict treatment allocation for participants at week 12. IEs will not be unblinded at the end of study. If needed, these ratings will be completed via a HIPAA compliant platform (i.e. Zoom).

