Prior to the PCAs, missing, invalid, and/or incomplete data will be removed. For SBI, observations missing one or more items on either CCC-2 subscale and/or greater than 30% of GEM items will be removed. For SC, observations with less than 50% of the responses (due to administrative error) on the RMET and/or DANVA2 will be removed. Provided these measures have high and near comparable component loadings on a single factor for each domain, thus confirming previous findings, they will be combined for separate composite scores for social behavior impairment (SBI) and social cognition (SC). To create the SBI composite score, total score on the GEM is reversed so that the higher scores reflect greater impairment as on the CCC-2. To create the SC composite score, percent correct was calculated for the RMET and DANVA-2 since they differ in total number of items and to adjust the denominator when all items were not presented due to administrative error. Subsequently, for each measure, scores will be standardized using the sample mean (and standard deviation) at baseline to account for change from baseline analyses, different and wide ranges of scores, and to ensure that composite scores across domains can be easily compared on the same scale (i.e., z-score). Following outlier detection (see below), standardized scores for each domain (SBI, SC) will then be averaged together to generate final composite scores at each time point. As such, a change in composite score reflects a change from baseline.

Outlier Detection. Individual scores from measures that are either influential points or outlier values (i.e., based on Cook's distance $> .5$ and/or Bonferroni-corrected outlier based on r-student residuals, respectively) and plausibly invalid (e.g., due to clinical reasons or administrative errors) will be removed. Composite scores will then be re-standardized and remaining extreme outliers (>3 SD above the mean for a specific timepoint) will be removed if they change the model significantly ($>10\%$ change in estimated values).

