Data Analysis. Primary: Composite scores of both primary outcomes (i.e., SBI and SC) will be used as the response (i.e., outcome) variable in a series of mixed-effects linear regression models using the *lmer* package in *R Studio* to assess the effect of treatment condition (ION-ASD vs. Facilitated Play), time (e.g., change from baseline after 12 weeks), and condition X time interaction. Across all models, the individual participant will be included as the random effect. Age, verbal IQ, ADHD and generalized anxiety (from the Child & Adolescent Symptom Inventory-5 [CASI-5] T-scores) will be entered into the model to be examined as potential covariates and/or moderators to outcomes as in prior work. We will estimate effect sizes (standardized Betas) and confidence intervals (95%) acknowledging the likelihood that analyses may not permit definitive conclusions given the likely size of the confidence intervals. Finally, if the statistical assumptions of the model are not met (e.g., homoscedasticity, normality, linear relationships), generalized linear models with appropriate link functions or potential transformations of predictor variables will be assessed.

Secondary Outcomes. The linear mixed-effects models will also be used on secondary outcome measures: SRS T-score, mean Caregiver Strain Global rating scale. Responder (i.e., Clinical Global Inventory-Improvement [CGI-I]) analysis will be conducted using either a Chi-squared or Fisher's exact test (when observations are small such that $>20\%$ of cells have *expected* count <5) on the number of responders (i.e., CGI-I scores of 1-2) versus non-responders (i.e., CGI-I scores of 5-7) by group.

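### The SAP lets a flagged score be removed for undefined clinical reasons before the co-primary composites are formed, with no masking rule and no analysis that keeps it

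*SAP*

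**What the plan says.** The SAP's Outlier Detection paragraph has two steps. This point concerns the first. It acts on "Individual scores from measures that are either influential points or outlier values", where the flag is Cook's distance above 0.5 and/or a "Bonferroni-corrected outlier based on r-student residuals, respectively". A flagged score that is also "plausibly invalid (e.g., due to clinical reasons or administrative errors) will be removed".

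The preceding paragraph of the SAP fixes the order. After outlier detection, "standardized scores for each domain (SBI, SC) will then be averaged together to generate final composite scores at each time point". Under Data Analysis, "Composite scores of both primary outcomes" are the response variables, so a first-step removal feeds straight into both co-primaries.

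The SAP does not define clinical reasons, name who judges validity, require masking to arm, identify the model that yields the residuals, or plan an analysis that retains the removed scores. The protocol has no outlier rule. Its Section 8.8 describes invalid or incomplete data only in terms of missing items. Its Termination Visit text (Section 5.2) asks for endpoint procedures at withdrawal so that an intent-to-treat analysis is possible.

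On masking, Protocol Section 3.6 says that "concealing treatment allocation to participants and treating clinicians is not possible", and Section 3.1 that "safety assessments will be conducted by unblinded treating medical clinicians". On side effects, Protocol Section 1 says of the team's open-label oxytocin study in adolescents: "Mild to moderate side effects were reported including irritability, headache, upper respiratory infections, and decreased appetite".

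**The concern.** The two examples of invalidity differ in kind. An administrative error means that the test did not measure the child. A clinical reason describes the child's state, and after randomisation that state may be a consequence of treatment. A child who scores badly because of irritability, illness or regression has a real outcome that belongs in the comparison.

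The ground can also apply unequally. Irritability is reported with oxytocin in Protocol Sections 1 and 1.1, and the facilitated play arm receives no drug (Section 5.1). Deleting outcomes for a reason that may depend on arm breaks the comparison that randomisation protects and conflicts with the intent-to-treat aim. Because no analysis keeps the removed scores, a reader of the results could not see how much they mattered.

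**Working it through.** **Inputs.** SD 0.670, difference 0.40, two-sided 0.05, and 25 per group with 5% attrition (Protocol Section 8.9). Phase 2 has 70 participants at 1:1, so 35 per arm (Section 3.1). SBI averages three measures (two CCC-2 subscales and the Griffith total) and SC averages two (RMET and DANVA-2), from the SAP.

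**The plan's own figure.** The stated 80% power is reproduced by a paired t test: 0.800 at n = 24 and 0.817 at n = 25. A two-group t test at 25 per arm gives 0.54. That is a separate matter. It matters here only because it shows that 0.67 behaves as the SD of a within-child change. Using it as the SD of change in each arm is an assumption.

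**Which scores are exposed.** The SAP does not name the model, so I assume a two-group model of change (two parameters, leverage h = 1/n, N = 2n).
- Bonferroni cutoff: the t quantile at 1 − 0.05/(2N) with N − 3 degrees of freedom is 3.51 at 25 per arm and 3.55 at 35 per arm.
- Cook's distance: D = (r²/2) × h/(1 − h) = r²/[2(n − 1)]. Setting D = 0.5 gives r = √(n − 1), which is √24 = 4.90 and √34 = 5.83.

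The Bonferroni flag fires first, so only scores about 3.5 SD out or more can reach the validity judgement.

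**Effect of one deletion on an arm mean.** Removing a child who lies d from the arm mean moves that mean by d/(n − 1). At 3.5 SD, d = 3.5 × 0.67 = 2.345.

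| Case | 25 per arm | 35 per arm |
|---|---|---|
| Whole composite that far out and lost | 2.345/24 = 0.098 (24% of 0.40) | 2.345/34 = 0.069 (17%) |
| One of three SBI measures lost, rest averaged | 0.098/3 = 0.033 (8%) | 0.069/3 = 0.023 (6%) |
| One of two SC measures lost, rest averaged | 0.098/2 = 0.049 (12%) | 0.069/2 = 0.034 (9%) |

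The last two rows assume that the child's other measures sit at the arm mean and that 0.67 also applies to a single measure. The SAP does not say whether a composite is still formed when one component has been removed, so both cases are shown.

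**When it matters.** I simulated 20,000 trials per scenario and removed every flagged bad ION-ASD change score outright. This is a worst case.
- Normal data, no treatment-caused extremes: a bad ION-ASD score is flagged in about 1.3% of trials, and a false finding of benefit stays at 2.5%.
- Assumed harm: every ION-ASD child improves by 0.268 and 8% also worsen by 5 SD. The true net effect is zero, since 0.08 × 5 × 0.67 = 0.268. With all scores kept, bias is 0.00 and false benefit occurs in 4.8% of trials (25 per arm) or 4.7% (35 per arm). With deletion, bias is −0.129 and 16.1%, or −0.122 and 17.9%.
- Same harm, flagged scores deleted in both arms and both directions: at 25 per arm, bias is still −0.129 and false benefit 16.1%. Masking the decision would therefore not be enough by itself.

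**The case against.** The strongest reply is that the rule has two conditions. A score must be statistically extreme and also plausibly invalid. Clinical reasons are only an example of why it might be invalid, not a licence to delete valid bad outcomes. A child who is ill or disengaged during the RMET or DANVA-2 may give a score that measures little, and the predecessor trial lost imaging data to compliance problems (Protocol Section 1.1). This is partly right, and the fix allows for a failed test session. But the SAP gives no criterion that separates a failed session from a real bad outcome.

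Four stronger readings are tempting and are not supported.
- A reader might infer that unmasked staff make the decision. The SAP is silent. Treating and safety clinicians know the arm, coordinators open the randomisation form, and the investigator both meets families about the drug and helps to monitor the database (Protocol Sections 3.1, 3.6, 5.1, 5.2 and 8.7). That makes unmasked judgement possible, not documented. The evaluators who collect the SC measures are masked.
- A reader might infer that the judgement follows sight of the primary result. The step comes before the composites are averaged, so their model cannot yet have been fitted on final data. The model behind the flag is unnamed and need not contain treatment.
- A reader might infer that the rule hides harm or favours oxytocin. It covers both arms and both directions, and adverse events are compared separately. The irritability reported was part of a mild to moderate profile, and nothing shows that it yields scores beyond 3.5 SD.
- A reader might size the effect with a 3 SD score. Such a score would generally not be flagged at this step.

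**Conclusion.** The flaw in the rule stands. As written, the first outlier step permits a real post-randomisation outcome to be removed on an undefined clinical ground, without masking and without an analysis that restores it, before both co-primaries are formed.

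The size is conditional. Few scores are exposed. One deletion at 3.5 SD shifts an arm mean by about 0.07 to 0.10 if the whole composite is lost, by about 0.02 to 0.03 for SBI, or by about 0.03 to 0.05 for SC, if the remaining measures are averaged. These figures rest on SD 0.67, 25 to 35 per arm and a simple two-group model of change. The direction cannot be predicted. The larger error rates in the simulation need assumed harm rates that the documents do not give. The SAP should be changed because the correction is cheap and the trial is small, not because bias in a given direction has been shown.

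**What to change.** Delete clinical reasons from the SAP's first outlier step. Allow a score to be removed only for an administration, equipment or scoring failure documented at the visit, including a test session recorded at that time as not validly completed. Have someone masked to arm decide before any model containing treatment is fitted.

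Keep every other flagged score in the primary analysis, report a sensitivity analysis without those scores, and list all removals by arm, measure and reason. State also whether a composite is formed when one of its measures has been removed.

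The cost is SAP wording and a short removal log. The downside is that a few noisy but real scores stay in, so the variance may be slightly larger.

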Caregiver reports on the ABC, PDDBI-SV, Griffith Empathy Scale, Children's Communication Checklist, CASI-5, Caregiver Strain, Vineland 3, SRS-2, RBS-R, and AIM will be collected at midpoint along with CGI-I ratings (blinded). Ratings may be conducted +/- 7 days from week 6 group depending on family schedules.

Week 12 (Endpoint)

The end of treatment visits occurs at Week 12 (to take place within \pm 7 days from the target date). At these visits, blood work, vital signs, temperature, height, weight, and an ECG will be completed. In addition, participants will undergo a series of assessments, which are anticipated to take approximately 4-6 hours to complete. The visit can be split into as many as three visits if this is better for the participant. The following measures will be completed: the CGI-I (Global and Social), the AE rating form, the Bates & Reilly Conversational Task, the CY-BOCS, Let's Face It, the RMET, the CASI-5, the RBS-R, the SRS, the ABC, the BFRT, the BASC-3, the PDDBI-SV, the Griffith Empathy Scale, the CCC, the Caregiver Strain, the DANVA2, the TAT, , and the GEMEP emotion recognition test, and sensor-based social-communication monitoring tests.

Week 16 & Week 24 (Maintenance visits 1 & 2)

There will be an additional follow-up appointment 12 weeks (\pm 7 days) after the participant stops taking the study drug. This visit is primarily to examine safety of OXT discontinuation, and look for possible maintenance of any favorable effects of ION-, and longer term safety. The assessments completed during this visit are identical to the Week 12/end of treatment visit.

Termination Visit: A participant may voluntarily withdraw from the study at any time. The PI has the right to discontinue a subject from this study or withdraws a participant from the study at any time. Every effort will be made to obtain information on subjects who withdraw. Participants who discontinue study drug prematurely will be asked to return to the clinic and complete all end of study safety lab work (week 12 blood work).

Participants will also be asked to complete all endpoint study procedures on their final visit before withdrawal to allow for true intent to treat analysis.

Missed Visits and Visit Windows

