8.8. Statistical analysis

Specific Aim 1 & Exploratory Aim 1: Safety and tolerability will be analyzed by analyzing for group differences on total scores and domains of the AE form and satisfaction surveys respectively. Efficacy analysis will be follow analytic procedures used to derive social behavior and social cognition composites for the Seaver-NETT RCT¹⁶. First, a principal components analysis with varimax (orthogonal) rotation will be conducted on subscales of the primary social behavior measures - Griffith Empathy Scale and CCC-2; and raw total scores on primary social cognition outcomes – RMET and DANVA2. The PCA is used to develop composite scores in a field with no viable outcomes for higher-order core social impairments as well as to minimize floor and ceiling artifacts, effects of variability in response, and other sources of measurement error. Variables with high factor loadings for subscales will be entered into composite score development for the social cognition and social behavior composites. Missing, invalid, and/or incomplete data (i.e. more than 30% items missing when not pre-defined by scale) will be excluded from the factor analysis.

A linear mixed model analysis will be conducted on all participants with at least two of four available time points (Wk 0, Wk 12, 1-mon, 3-mo). Composite scores of co-primary outcomes social behavior and social cognition will be used as the response variable; treatment condition, time, and condition * time interactions will be covariates. Verbal IQ will also be entered into the model in exploratory moderator analyses. We will estimate effect sizes (Cohen's d) and confidence intervals (95%) acknowledging the likelihood that analyses may not permit definitive conclusions given the likely size of the confidence intervals.

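### The second outlier step deletes co-primary scores nobody has judged invalid, and does so according to how far they move an unnamed model estimate

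*SAP*

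**What the plan says.** Step 1 of the SAP's Outlier Detection section looks at scores on the individual measures. A score flagged by Cook's distance or by a Bonferroni-corrected residual test is taken out only if a second condition also holds: it must be flagged "and plausibly invalid (e.g., due to clinical reasons or administrative errors) will be removed".

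Step 2 re-standardizes the composites and then states that "remaining extreme outliers (>3 SD above the mean for a specific timepoint) will be removed if they change the model significantly". The bracket that follows sets the limit at a change of more than 10%. It does not say which estimate is meant, which of the several models, or whether scores are tested singly or together.

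The SAP's Data Analysis section makes these composites, social behavior impairment (SBI) and social cognition (SC), the response variables for both primary outcomes. The models contain condition, time and their interaction, with participant as the random effect and further covariates to be examined. On SBI a high score is bad: "total score on the GEM is reversed so that the higher scores reflect greater impairment as on the CCC-2". SC is built from percent correct, so a high score is good.

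The protocol has no outlier rule. Section 8.8 says only: "Missing, invalid, and/or incomplete data (i.e. more than 30% items missing when not pre-defined by scale) will be excluded from the factor analysis". Section 5.2 (Termination Visit) asks withdrawing participants to "complete all endpoint study procedures on their final visit before withdrawal to allow for true intent to treat analysis". Neither document asks for the primary result to be shown without step 2.

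**The concern.** Step 2 reaches only scores that survived step 1, so by construction it acts on data nobody has judged invalid. There are two difficulties.

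- **The data can depend on the result.** If the 10% limit refers to the condition-by-time estimate, it is relative to the effect itself. The same extreme score is then more likely to be deleted when the estimated effect is small than when it is large. If it refers to any coefficient in the model, almost any eligible score will meet it. Two analysts could both follow the SAP and analyse different data.
- **The rule is one-sided as worded.** Only scores *above* the mean qualify. On SBI these are the most impaired children, so marked worsening can be deleted while marked improvement stays. If the authors meant *away from* the mean, this second point falls and the first stands.

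The treatment estimate suffers when extreme scores are unequal between arms. Removals then come mainly from one arm and move the estimate for or against ION-ASD. Only the co-primary efficacy composites are at issue, because safety is analysed from the AE form.

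**Working it through.** **Inputs.** From the protocol: 35 per arm (section 3.1, Phase 2 n=70, allocated 1:1) and a difference of 0.40 (section 8.9). Assumed: 0.40 is in composite units, composite SD 0.85, within-child correlation 0.7. Negative SBI differences favour ION-ASD. The plan gives no figure for step 2 itself. The 80% power stated beside the 0.40 reproduces as a one-sample or paired t-test with 24 evaluable children (25 × 0.95 = 23.75; power 0.800), but nothing below depends on it.

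**Model.** Random-intercept REML with arm, time and arm × time, using baseline and Week 12, or those plus Weeks 16 and 24. Scores with z > 3 at a timepoint are dropped if the arm × Week 12 estimate moves by more than 10%.

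**1. Is the limit easy to reach?** Deleting one score z SD from its arm mean shifts that mean by z/(n-1). For z = 3 this is 3/39 = 0.077 SD with 40 per arm and 3/24 = 0.125 SD with 25 per arm. If 0.40 is in SD units, these are 19% and 31% of it.

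**2. Does deletion depend on the effect?** Both arms have the same distribution shape, 35 per arm. Percentage of trials in which the 10% limit on condition × time is met, given an eligible score:

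| Version | Normal: no effect / 0.40 | t (4 df): no effect / 0.40 |
|---|---|---|
| Two timepoints, drop single score | 93 / 54 | 82 / 49 |
| Two timepoints, drop whole child | 78 / 25 | 74 / 36 |
| Change score | 78 / 26 | 73 / 36 |
| Four timepoints | 52 / 24 | 61 / 32 |

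A separate t (4 df) simulation gave 91 / 64. The rate is lower with 0.40 in every version. If any fixed coefficient counts, the limit is met in about 99% of eligible trials with no effect and 96–99% with 0.40.

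**3. What if extreme scores are unequal between arms?** A child displaced by k SD at Week 12 moves the arm mean by k × SD/n = 4 × 0.85/35 = 0.097. If the effect is otherwise -0.40, the full-data value is -0.40 + 0.097 = -0.303 (simulated -0.304). The rule fired in 68.4% of runs, so the expected value after it is about -0.303 - 0.684 × 0.097 = -0.369 (simulated -0.371).

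| SBI scenario, 35 per arm | All data | After step 2 |
|---|---|---|
| One ION-ASD child worsens 4 SD | -0.30 | -0.37 |
| Same, four timepoints | -0.31 | -0.37 |
| Same, 3 SD (fires in 36%) | -0.33 | -0.36 |
| Same, correlation 0.5 to 0.8 | -0.31 | -0.38 |
| Same, composite SD 1 | -0.28 | -0.37 |
| Same, 25 per arm | -0.26 | -0.35 |
| One ION-ASD child improves 4 SD, as worded | -0.50 | -0.50 |
| Same, if both tails are meant | -0.50 | -0.42 |
| One control child worsens 4 SD | -0.50 | -0.42 |
| Two ION-ASD children worsen 4 SD, no other effect | +0.19 | +0.06 |
| Two ION-ASD children improve 4 SD, no other effect, as worded | -0.20 | -0.20 |

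**4. What if both arms share one distribution?** The mean estimate moves by at most 0.002. The largest coverage change is 94.7% to 94.4%.

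**5. How often would step 2 delete anything?** For one outcome and two timepoints, deletion occurs in about 3–11% of trials with normal scores and 25–40 per arm. With t (4 df) scores it is about 17–49%, depending on how the heavy tail is built and on the true effect. With skewed scores it is 32–61%.

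**6. Does it reach SC?** A child at 100% on both tests has z = ((100 - mean)/SD)/√((1 + r)/2). With mean 70, SD 12 and r = 0.5 this is 2.5/0.866 = 2.89. Means of 60–75% and SDs of 10–15 points give 1.9 to 4.6. The cut-off may be unreachable, so no effect on SC is claimed.

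**The case against.** The rule is prespecified and numeric, and it responds to the size of a change rather than its direction or p-value. Applied mechanically to one estimate, it leaves type I error at 0.047–0.053 in simulation. That stands, which is why no bias, coverage or error-rate harm is claimed for equal distributions.

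The shifts in section 3 of the working come from planted scores. In each case where the rule acts, the estimate moves toward the effect in the other children. In the one-child ION-ASD case, root mean squared error around -0.40 falls from 0.185 to 0.165. This is harm only if the extreme response belongs to the effect being estimated. When nobody has found the score invalid, an intent-to-treat reading says it does. That reading is inferred: section 5.2 concerns collecting data at withdrawal, and section 8.8 is silent on outliers and itself requires two timepoints. The documents do not contradict each other outright.

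A 4 SD score would usually be flagged at step 1 (about 93% of runs in a composite-level approximation), so the figures assume that it passes the invalidity review. SBI is also bounded, and whether 3 or 4 SD can be reached is untested. If it cannot, step 2 never acts and removing it costs nothing.

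Finally, naming the estimate and the tails and reporting both results would cure the ambiguity. It would still leave a primary data set chosen by its effect on the fit.

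**Conclusion.** The concern holds. Step 2 can remove co-primary scores that have not been judged invalid, on a criterion tied to an unspecified fitted estimate, and the unaltered result need not be reported.

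The size is conditional. One extreme child in one arm moves the SBI estimate by roughly 0.03 to 0.09 across the versions in which the rule acts. Two ION-ASD children who worsen have about two thirds of their apparent harm removed ((0.19 - 0.06)/0.19 = 68%). These figures rest on the assumed composite SD, correlation and planted scores, and they illustrate what can happen rather than forecast it. The asymmetry between worsening and improvement rests on reading *above* literally.

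This should be changed, but it does not by itself invalidate the primary analysis. It matters more here because the SAP's output is mainly estimates and confidence intervals from a small sample.

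**What to change.** - Delete the removal rule in step 2 and keep every score not judged invalid in the primary analysis. The re-standardization in the same sentence can stay if it is wanted.
- Keep the step 1 statistical flags, but pass only the flagged participant numbers and visits, without arm or model output, to existing staff blind to arm, who judge plausible invalidity. An independent evaluator who did not test that child is one option, since protocol section 3.6 states: "IEs will not be unblinded at the end of study".
- Always report one prespecified sensitivity analysis that leaves out composite scores with |z| > 3 at a timepoint, in both tails and with no 10% trigger.

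The cost is one deleted rule, a small wording change to step 1 and one extra model fit per outcome. The primary interval may be wider. With equal distributions the mean SE with all data against the rule was 0.157 against 0.157 (normal) and 0.155 against 0.152 (t, 4 df), so 0–2% wider. If one 4 SD score stays in, it is about 11% wider (0.184/0.166 = 1.11).
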